7.1 Ethical Considerations: Informed Consent/Assent and HIPAA Authorization

Ethical Considerations

This study is to be conducted in accordance with applicable US government regulations and international standards of Good Clinical Practice, and applicable institutional research policies and procedures. This protocol and any amendments will be submitted to a properly constituted Institutional Review Board (IRB) or independent Ethics Committee (EC) in agreement with local legal prescriptions, for formal approval of the study conduct. The decision of the IRB/EC concerning the conduct of the study will be made in writing to the investigator and a copy of this decision will be provided to the sponsor before commencement of this study. The investigator should provide a list of IRB/EC members and their affiliate to the sponsor.

7.2 Institutional Review Board (IRB) Review

All subjects for this study will be provided a consent form describing this study and providing sufficient information for subjects to make an informed decision about their participation in this study. This consent form will be submitted with the protocol for review and approval by the IRB/EC for the study. The formal consent of a subject, using the IRB/EC-approved consent form, must be obtained before that subject undergoes any study procedure. The consent form must be signed by the subject and the investigator-designated research professional obtaining the consent.

7.3 Subject Confidentiality

Information about study subjects will be kept confidential and managed according to the requirements of the Health Insurance Portability and Accountability Act of 1996 (HIPAA). Those regulations require a signed subject authorization informing the subject of the following:

- What protected health information (PHI) will be collected from subjects in this study.
- Who will have access to that information and why.
- Who will use or disclose that information.
- The rights of a research subject to revoke their authorization for use of their PHI.

In the event that a subject revokes authorization to collect or use PHI, the investigator, by regulation, retains the ability to use all information collected prior to the revocation of subject authorization. For subjects that have revoked authorization to collect or use PHI,

attempts should be made to obtain permission to collect at least vital status (i.e. that the subject is alive) at the end of their scheduled study period.

7.4 Deviations/Unanticipated Problems

Protocol deviations or violations (includes intentional and accidental/unintentional deviations from the IRB approved protocol) for any of the following situations:

- One or more participants were placed at increased risk of harm
- The event has the potential to occur again
- The deviation was necessary to protect a subject from immediate harm

In the event of a significant deviation from the protocol due to an emergency, accident, or mistake (e.g., violation of informed consent process, IMP dispensing or subject dosing error, treatment assignment error, subject enrolled in violation of eligibility criteria or concomitant medication criteria), the investigator or designee will contact the sponsor or designee at the earliest possible time by telephone. The investigator, medical monitor and sponsor will come as quickly as possible to a joint decision regarding the subject's continuation in the trial. This decision will be documented by the investigator and the sponsor, and reviewed with the Data Safety Monitor.

7.5 Data Collection

The documentation into the source documents for research visits should occur in real time and no later than 3 business days from the date of the visit. If the documentation is later than three business days, this should be considered a late entry with an explanation. Documentation of the data should occur within 7 business days of the visit. If not entered within that time period, we will document in the source documents the reason for the delay.

Source Documents

Source data is all information, original records of clinical findings, observations, or other activities in a clinical trial necessary for the reconstruction and evaluation of the trial. Source data are contained in source documents. Examples of these original documents, and data records include: hospital records, clinical and office charts, laboratory notes, memoranda, subjects' diaries or evaluation checklists, pharmacy dispensing records, recorded data from automated instruments, copies or transcriptions certified after verification as being accurate and complete, microfiches, photographic negatives, microfilm or magnetic media, x-rays, subject files, and records kept at the pharmacy, at the laboratories, and at medico-technical departments involved in the clinical trial.

Case Report Forms

The study case report form (CRF) is the primary data collection instrument for the study. All data requested on the CRF must be recorded. All missing data must be explained. If a space on the CRF is left blank because the procedure was not done or the question was not asked, write "N/D". If the item is not applicable to the individual case, write "N/A". All entries should be printed legibly in black ink. If any entry error has been made, to correct such an error, draw a single straight line through the incorrect entry and enter the correct data above it. All such changes must be initialed and dated. DO NOT ERASE OR WHITE OUT ERRORS. For clarification of illegible or uncertain entries, print the clarification above the item, then initial and date it.

Records Retention

It is the investigator's responsibility to retain study essential documents for at least 2 years after the last approval of a marketing application in their country and until there are no pending or contemplated marketing applications in their country or at least 2 years have elapsed since the formal discontinuation of clinical development of the investigational product. These documents should be retained for a longer period if required by an agreement with the sponsor. In such an instance, it is the responsibility of the sponsor to inform the investigator/institution as to when these documents no longer need to be retained.

7.6 Data Quality Assurance

The principal investigator has ethical, legal, and scientific obligations to follow this trial in accordance with established research principles, the ICH E6 GCP: Consolidated Guidance, and applicable regulatory requirements and local laws. The investigator will ensure all research staff working on this protocol meet the acceptance of the IRB. In addition, all investigators and clinical site personnel will undergo initial and ongoing training for this clinical trial. The training will be documented on training logs.

Either institution or senior research staff may conduct quality assurance audits. Audits will include, but are not limited to: IMP supply, presence of required documents, the informed consent process, and comparison of the data in REDCap against the paper source documents. The senior research staff, investigator or co-investigator will also spot check charts, REDCap, and sign off on completed subjects.

During each subject's visit to the clinic, research staff will record progress notes to document all significant observations. The investigator or co-investigator will sign these notes at each visit.

At a minimum, these notes will contain: documentation of the informed consent process, any revised consents, eligibility (inclusion/exclusion criteria prior to study medication administration), date of the visit and the corresponding visit in the trial schedule. The note will also include the presence or absence of adverse events (severity, frequency, duration, action taken, outcome and relationship to study medication as assessed by the investigator/co-investigator). Notes will also include changes in concomitant medications or dosages. Included in the progress note will be all telephone numbers or other means of contact that provide any significant clinical information. Source documents and source data will meet the same fundamental elements of data quality (e.g. attributable, legible, and accurate)

This study will use NYU Tisch Laboratory. We will rely on their list of normal and abnormal values and will maintain all laboratory information in regulatory binder. We will use an NYU cardiologist to read all EKGs and respond with clinical judgement to the investigator regarding inclusion or exclusion of subjects in accordance with Good Clinical Practices.

We will retain all standard operating procedures in the essential documents folder and will also circulate among the staff at start of the project and at each amended change.

7.7 Study Records

Source Documents

Source data is all information, original records of clinical findings, observations, or other activities in a clinical trial necessary for the reconstruction and evaluation of the trial. Source data are contained in source documents. Examples of these original documents, and data records include: hospital records, clinical and office charts, laboratory notes, memoranda, subjects' diaries or evaluation checklists, pharmacy dispensing records, recorded data from automated instruments, copies or transcriptions certified after verification as being accurate and complete, microfiches, photographic negatives, microfilm or magnetic media, x-rays, subject files, and records kept at the pharmacy, at the laboratories, and at medico-technical departments involved in the clinical trial.

Case Report Forms

The study case report form (CRF) is the primary data collection instrument for the study. All data requested on the CRF must be recorded. All missing data must be explained. If a space on the CRF is left blank because the procedure was not done or the question was not asked, write "N/D". If the item is not applicable to the individual case, write "N/A". All entries should be printed legibly in black ink. If any entry error has been made, to correct such an error, draw a single straight line through the incorrect entry and enter the correct data above it. All such changes must be initialed and dated. DO NOT ERASE OR WHITE OUT ERRORS. For clarification of illegible or uncertain entries, print the clarification above

7.8 Access to Source

The source documents will be all the clinical findings and observations collected either on the actual scale or on the specific source documents for each study visit. This will include all the laboratory and EKG results. The results of the documents will be entered into REDCap and rechecked for accuracy. The REDCap form will have a check off at the bottom of the page indicating completion of entry into REDCap REDCap is a secure web application used to collect virtually any type of data (including 21 CFR Part 11, FISMA, and HIPAA-compliant environments). REDCap supports online or offline data capture for research studies and operations. De Identified Data in REDCap can be exported into excel sheets for analysis.

Subjects are called three times a day from an NYU mobile device. TASS information will be entered directly into redcap via network desktop

[name] will conduct the statistical analysis of this study.

[name]. Professor of Psychiatry and of Neuroscience & Physiology SUNY Upstate Medical University [name] [contact] [contact], [contact] (fax)

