6.1.2. Dosage, Admin, Schedule

During the two-week, single-blind, placebo lead-in, all subjects will receive 12.5mg placebo at Visit 1 (Baseline) and Visit 2 (Week 1 Placebo Lead in).

During four-week, treatment period, Mydayis will be initiated at a dose of 12.5mg/day at Visit 3 and can be titrated up (in the judgment of the investigator) in increments of 12.5mg, based upon clinical response and tolerability. Dose increases up to 25mg at Visit 4, up 37.5mg at Visit 5 and holds at the dose from Visit 5 of up to 37.5mg at Visit 6. Note there is no dispensing on Visit 7; last in clinic/remote visit.

Patients will be seen weekly throughout the trial. Participants are given dosing instructions and will return to the clinic weekly for review of compliance. Subjects must have over 80% compliance to continue in the study.

Compliance will be tracked by counting the remaining pills in the bottle at each visit. Subjects are reminded to bring back their pills and empty bottles at each visit. Subjects are instructed that noncompliance without the doctor's approval would be dangerous. It may warrant reevaluation of their continued participation.

Investigational pharmacy will accept and document returns from research team/subjects. The Investigational Pharmacy will also dispense study medication to the research team/subjects.

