6.1.8 Restrictions

Subjects will be screened for drug and alcohol abuse during the prescreen phase. Subjects are instructed on the dangers of drinking alcohol or engaging in drug use during treatment with Mydayis. They will be warned not to use Mydayis for any other condition except the condition for this study: ADHD. Subjects will be instructed and reminded at each study visit not to share this medication with other people, even if they have ADHD. They will be reminded that the Mydayis may harm those for who it is not prescribed for and it is against the law. Subjects will be reminded to report any adverse events or concomitant medications they are taking at each visit.

Subjects will be reminded to take their medication at 5am each morning, as the study assessments are dependent on the consumption of Mydayis at 5:00 am.

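### The 14-15 h TASS rating cannot be tied to hours since dose: the protocol's windows allow 12-16 h, and the supplied text requires no record of dose time or call time

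*Combined protocol and SAP*

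**What the plan says.** **Purpose.** Sections 1.1 and 3.2 make TASS ratings 14-15 h after the morning dose a stated aim, and section 4.3 lists them as a secondary objective.

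**Timing.** Section 6.1.8 has patients reminded to dose at 5 am, "as the study assessments are dependent on the consumption of Mydayis at 5:00 am". Sections 6.3, 6.3.5 and 6.3.6 recommend dosing at 5 am +/- 1 h. They place the three TASS ratings at 5:30-6 am, 9 am and 7 pm, each +/- 1 h, labelled half to one hour, 4 h and 14-15 h post dose.

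**Adherence.** Section 6.1.2: "Compliance will be tracked by counting the remaining pills in the bottle at each visit". Compliance must exceed 80%. Sections 6.3, 6.3.5 and 6.3.6 also expect patients to report taking at least 80% of doses.

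**Capture and checking.** Section 7.8 says: "Subjects are called three times a day from an NYU mobile device. TASS information will be entered directly into redcap via network desktop". The same section describes source as findings "collected either on the actual scale or on the specific source documents for each study visit", and adds: "The results of the documents will be entered into REDCap and rechecked for accuracy". Section 7.6 opens its list with "Audits will include, but are not limited to" and names, among other items, "comparison of the data in REDCap against the paper source documents".

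**Analysis.** Sections 6.4.1, 6.4.3.1, 6.4.3.2 and 6.4.4 analyse the TASS by the slots 1 h, 4 h and 14-15 h. Except for 6.4.3.2, which only lists the variables, they specify the ITT sample. Section 6.4.5 carries the last observation forward, and section 6.4.3.7 says nothing further will be analysed.

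**The concern.** A claim about effect at 14-15 h needs hours since dose to be known for each rating. The plan fixes the dose and the call by separate clock windows and then analyses by label. A rating made 12 or 16 h after the dose, or on a day when no dose was taken, enters the same slot as one made at 14.5 h. Without the two times, nobody can later say which is which.

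At stake are the 14-15 h TASS result and the within-day comparison of slots. The AISRS total, which is the primary measure in sections 4.2, 5.1 and 6.4.4, is not affected. Section 6.4.1, however, names the TASS-AISRS correlations as primary; on that wording the problem reaches the primary outcome.

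**Working it through.** **1. Does the nominal schedule give the label?** 5 am to 7 pm is 14 h, the lower edge of 14-15 h.

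**2. What do the windows allow?** Shortest interval = earliest call - latest dose; longest = latest call - earliest dose. The dose window is 04:00-06:00.

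| TASS | Call window | Shortest | Longest | Label |
|---|---|---|---|---|
| First | 04:30-07:00 | 4.5 - 6 = -1.5 h | 7 - 4 = 3 h | 0.5-1 h |
| Second | 08:00-10:00 | 8 - 6 = 2 h | 10 - 4 = 6 h | 4 h |
| Third | 18:00-20:00 | 18 - 6 = 12 h | 20 - 4 = 16 h | 14-15 h |

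So a first call inside its window can precede the dose, and the first and second slots can overlap (2-3 h).

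**3. How many third calls would be at 14-15 h?** Assume dose and call times are independent and uniform in their windows. Elapsed time t then has density (2 - |t - 14|)/4 on 12-16 h.
- Within 14-15 h: (2 - 0.5)/4 = 0.375, or 37.5%.
- Before 14 h: 50%.
- After 15 h: (1/2)/4 = 12.5%.

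A simulation of 10^6 draws gave 37.5%, 50.0% and 12.5%. With every dose at exactly 5:00, calls fall at 13-15 h and half are at 14-15 h. The documents do not give the real distribution of times.

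**4. Can the pill count fill the gap?** One dose missed in seven days is 6/7 = 85.7%, which passes the 80% rule; two is 5/7 = 71.4%, which fails. Over 28 days, five missed is 23/28 = 82.1%, which passes. A missed dose on a rating day can therefore pass. If the previous day's dose was taken, that evening's rating is 24 + 14 to 24 + 15 = 38-39 h after the last dose. The count shows neither which day was missed nor when a dose was taken, and the patient's overall report of 80% does not either.

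**5. Is the time recorded elsewhere?** The minimum visit note in section 7.6 includes the visit date, adverse events and medication changes, but not dose time or call time. Section 7.5 allows up to 3 business days for source entry and 7 for data documentation, so a REDCap time stamp need not equal the rating time.

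**The case against.** Several points on the other side stand.

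- A reader might infer from direct entry that the TASS has no paper source. The documents do not say so: the general rule in section 7.8 names the scale itself or the visit source documents. The two statements need reconciling.
- A reader might infer that the audit cannot detect mistimed ratings. The section 7.6 list is open-ended, and section 7.11 adds weekly chart review, monthly REDCap spot-checks and a monitoring plan that was not supplied. What can be said is that the named paper-to-REDCap comparison checks transcription, and it cannot check a time that was not recorded.
- A reader might infer that time stamps are always late. Direct entry may well happen during the call; section 7.5 only permits a delay.
- Dose and call times may already be on the REDCap form or in the call script. The case report forms were not supplied, nor were the attachments listed under Appendices.
- The label may be meant to govern, with the clock time only as a guide. But a call placed 14-15 h after the actual dose requires knowing that dose time. Under both rules together, a 6 am dose (6 + 14 = 20:00) leaves only 8 pm.

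The most tempting stronger reading is a specific loss of power. The plan's own figure reproduces: a paired t-test with n = 32, d = 0.6 and two-sided 5% has noncentrality 0.6 x sqrt(32) = 3.39 and power 90.8%, against a stated 90% or more. If one evening rating in seven were undosed with no residual effect, d would be 0.6 x 6/7 = 0.514 and power 80.5% (78.8% with the added mixture variance). That needs every patient to miss one dose a week on random days, although rating days include a call scheduled soon after dosing. It also borrows d = 0.6 from the general baseline-to-endpoint statement and replaces the planned regression on week with a single paired test. The documents support none of these steps, so the figure should not be used.

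**Conclusion.** The point holds as a gap in timing. The plan makes 14-15 h central, but its own windows permit 12-16 h. The supplied text requires no dose time, same-day dose confirmation or call time, and gives no rule for off-window or undosed ratings. The 12-16 h range is arithmetic on the stated windows and needs no assumption; the 37.5% rests on independent uniform times. That mistimed ratings would be analysed as 14-15 h follows from the plan's silence together with its nominal slots; no rule says so outright.

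The effect on the estimate and on power is not quantifiable from the documents. The change is worth making because unrecorded times cannot be recovered later. If the form already holds these fields, the remaining work is a cross-reference, the source and audit wording, and the analysis.

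**What to change.** 1. **Section 7.8:** add two required REDCap fields at every TASS call: the patient's reported time of that day's dose (or not taken) and the call start time. If the form already has them, cite it.
2. **Sections 7.8 and 7.6:** reconcile direct entry with the general source rule, name the TASS source, and match the audit to it.
3. **Section 6.3 and related visit text:** reconcile the clock windows with the post-dose labels so that the two describe the same interval.
4. **Section 6.4.3:** keep the ITT nominal-slot analysis with all ratings. Add a prespecified analysis of the 14-15 h and within-day TASS on actual hours since dose. Flag undosed days and examine them in a sensitivity analysis, and state that they are not filled by LOCF under section 6.4.5. Dropping them from the main analysis would select on adherence after baseline and conflict with the stated ITT rule.

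**Cost:** one extra question in a call already being made, one call-time entry, one more analysis and some wording. Dose time would remain self-reported.

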7.9 Data or Specimen Storage/Security

In this study, data will be collected, stored (digital, hard copy, etc.) and maintained in a secure manner (encryption, password protection, etc.).Only minimal information will be collected from the prescreens. Prescreens will be shredded after all necessary information is collected. The prescreens of those who have passed to screening will be added to a source chart and stored in a locked cabinet in a locked room until eligibility is determined. Once eligible, the subject is baselined and all source documents are stored in the same manner in a locked room in a locked cabinet. Data will be entered into the secure data capture system REDCap. Unidentified data will also be stored in our shared drive for writing purposes.

7.10 Retention of Records

Records Retention

It is the investigator's responsibility to retain study essential documents for at least 2 years after the last approval of a marketing application in their country and until there are no pending or contemplated marketing applications in their country or at least 2 years have elapsed since the formal discontinuation of clinical development of the investigational product. These documents should be retained for a longer period if required by an agreement with the sponsor. In such an instance, it is the responsibility of

the sponsor to inform the investigator/institution as to when these documents no longer need to be retained.

7.11 Study Monitoring

This study will be monitored according to the **monitoring plan**. The investigator will allocate adequate time for such monitoring activities. The investigator will also ensure that the monitor or other compliance or quality assurance reviewer is given access to all the above noted study- related documents and study related facilities (e.g. pharmacy, diagnostic laboratory, etc.), and has adequate space to conduct the monitoring visit.

[name], as PI, will be responsible for review of all aspects of the study at our site, and will review subject progress weekly, including:

- Recruitment procedures
- Informed consent
- Protocol violations
- Occurrence and handling of adverse effects
- Patient Outcomes
- Participants' safety, privacy and confidentiality
- Study progress toward recruitment goals and participant retention/attrition rates
- Review of new scientific literature pertinent to the safety of participants

All subject source charts will be reviewed for accuracy and completeness on a weekly basis by research staff. Subject REDCap data will be spot-checked by research staff once a month for any discrepancies and for completion.

[name] will determine whether risk/benefit ratios have changed to the extent that the trial should be modified or discontinued. Specific recommendations for protocol modifications, should they be necessary, will be elaborated, with accompanying rationale for each. This will be reported to sponsor, IRB, Study Monitor and manufacturers who will donate the study drug (Shire Pharmaceuticals Group plc.)

